## Tool Revision History

Version Number: 1

Version Date: 11/13/2018

Summary of Revisions Made:

Version Number: 2

Version Date: 12/21/2018

Summary of Revisions Made:

Version Number: 3

Version Date: 1/14/2019

Summary of Revisions Made:

Version Number: 4

Version Date: 2/20/2019

Summary of Revisions Made: Timing of cortisol collection, revised lab stress task and addition of attention task (SART), added description of Portland research space, adjusted SME and MBRT session length, blood pressure monitor equipment change.

Version Number: 5

Version Date: 3/6/2019

Summary of Revisions Made: Added stressor task to assessment flowchart and revised SME and MBRT session language.

Version Number: 6

Version Date: 3/12/2019

Summary of Revisions Made: Corrected typos to content added in Version 5.

Version Number: 7

Version Date: 6/3/2019

Summary of Revisions Made: Updated study locations, removed cortisol awakening response, added two new assessments (MAIA II and PASA), updated procedures for stress challenge including repeating measure at 3-month follow-up visit. Added Project Coordinator, [name] to study roster.

Version Number: 8

Version Date: 6/18/2019

Summary of Revisions Made: removed “informed” from verbal consent for phone screening, and removed “with saliva collection aid” from description of cortisol measurement.

Version Number: 9

Version Date: 7/15/2019

Summary of Revisions Made: Updated list of self-report measures and schedule of evaluations, added “Screen” box to participant flow diagram, added website, removed full-time and active status eligibility requirements (part-time LEOs may be eligible and “active status” is redundant with being a LEO), added description of the Social Evaluative Cold Pressor Task and saliva collection procedures, revised focus group question about saliva collection procedures.

Version Number: 10

Version Date: 8/27/2019

Summary of Revisions Made: Revised inclusion criteria to add “...at the rank of Sergeant or below,” extended assessment windows from 2 weeks to 3 weeks (for pre-, post-, 3-month followup, and 6-month followup), added Omron HEM-907XL to calibrate blood pressure at all assessment visits.

Version Number: 11

Version Date: 11/5/2019

Summary of Revisions Made: Added statement that if needed, we will recruit officers from Greater Portland and Albuquerque Metro areas in addition to Albuquerque Police Department and Portland Police Bureau; revised randomization allocation ratio from 1.5:1:1 to 2:1.5:1 for MBRT, SME, and NIC conditions, respectively; updated saliva collection timeframes.

Version Number: 12

Version Date: 7/1/2020

Summary of Revisions Made:

Due to COVID-19-related restrictions, screening, informed consent, and enrollment will all be via phone, REDCap and/or email. Assessment sessions and focus group procedures will be administered remotely to avoid in-person contact with participants. If state, local and university policies allow, intervention MBRT sessions 1 and 7 will be delivered in person at the respective study sites. If not, these sessions will also be conducted using the online Zoom platform. All SME sessions will be conducted online. Physiological lab-based assessments (HR, BR, sAA and cortisol) and stress induction (SECPT) will no longer be administered. A home-administered dried blood spot analyses assessing inflammatory cytokines was added at baseline, postcourse and 3-month assessment periods. Previous random sampling of participants to invite to participate in focus groups changed to inclusion of all participants in individual feedback phone interviews. Previously separate site-based intervention teams shifted to using the same pairs of interventionists at both sites. iMINDr software will be replaced with Ilumivu software.

Audio recording of sessions is now audio and video recording of sessions.

Version Number: 13

Version Date: 12/8/2020

Summary of Revisions Made: Added Madison Police Department as a recruitment site and [name] (University of Wisconsin Madison) as a co-investigator.

## PRÉCIS

### **Mindfulness-Based Resilience Training for Aggression, Stress and Health in Law Enforcement Officers**

#### **Objectives**

The primary objective of the study is to identify, optimize and refine best clinical and research practices to ensure success in a future multisite efficacy trial assessing effects of Mindfulness-Based Resilience Training (MBRT) versus attention control, Stress Management Education (SME), and a no intervention control on physiological, behavioral, and psychological outcomes among LEOs. The study's specific primary objectives are to ensure efficiency, optimization and fidelity of all procedures across all study sites.

#### **1: Enhance efficiency of recruitment, engagement, and retention across sites**

- 1.1 Refine recruitment methods used in our recent R21 trial to maximize inclusion of female and ethnic minority LEOs
- 1.2 Enhance previous R21 procedures to ensure  $\geq 80\%$  LEO retention throughout intervention and follow-up phases
- 1.3 Enhance participant treatment engagement and compliance to treatment protocol
- 1.4 Identify recruitment and retention barriers, and appropriately refine procedures

#### **2: Ensure fidelity and equivalence of lab, assessment, and data management procedures across sites**

- 2.1 Assess and improve efficiency of data collection and procedures for on-the-job LEO excessive use of force (e.g., aggressive drawing and discharge of weapons, vehicle rams, and illegal takedowns)
- 2.2 Confirm acceptability of self-report (resilience, aggression, burnout, depression, suicidal ideation, trauma, and alcohol misuse) and stress-related proinflammatory biomarkers (C-reactive protein [C-RP], interleukin 6 [IL-6], interleukin 10 [IL-10], tumor necrosis factor-alpha [TNF- $\alpha$ ]) data collection
- 2.3 Train relevant study staff in REDCap and confirm compliance with Good Clinical Practice procedures

#### **3: Optimize intervention training procedures and ensure fidelity to intervention protocols across sites**

- 3.1 Refine training and supervision procedures for clinical interventionists to enhance intervention fidelity
- 3.2 Hone session coding procedures and adapt the Adherence and Competence Scale for use with both MBRT and SME to ensure fidelity and equivalence across sites and the two active interventions

[figure not shown]
#### **4: Assess participant experience and optimize outcome measures across sites**

- 4.1 Qualitatively evaluate feasibility, acceptability, and impact of assessments, protocol, and interventions
- 4.2 Confirm sensitivity, responsiveness to change, and psychometric soundness of outcome measures

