#### **Objective 4: Assess participant experience and optimize outcome measures across sites.**

Well-developed content themes with data saturation emerging from feedback interviews will provide information on acceptability, impact of assessments, protocol and intervention fidelity, and equivalence of these markers across sites. Benchmark sensitivity and responsiveness values will determine the most sensitive and responsive measures relative to all study outcomes, versus a significance testing approach in which standardized/conventional threshold values are used to make decisions regarding significance. Sensitivity and responsiveness information will determine which outcomes are most impacted by MBRT for retention in a future full-scale multi-site efficacy trial. Benchmarks for equivalence across sites will be evidenced by: a) qualitative themes that suggest experiential continuity across sites, and b) equivalence in outcome measure response distributions, reliability estimates, and intraclass correlations.

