Participants randomized to the NIC condition will not receive any intervention, but will participate in the same assessments as the two active intervention conditions (i.e., at baseline, post-intervention, 3- and 6-month follow-up). Assessment times will be yoked to those of the two active intervention conditions.

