## **9.5 Outcomes**

Outcomes will be analyzed using quantitative analyses (sensitivity and responsiveness) after creating composite scores for self-report measures and physiological outcomes. For behavioral data, we will analyze individual behavioral items as well as a composite score.

Committee oversight of outcome analyses and results is not included in our protocol (oversight of AE information is discussed above in section 9.4). However, Drs. [name] (Portland) and [name] (Albuquerque) will review all data collection forms on an ongoing basis for data completeness and accuracy as well as protocol compliance. The primary source of research materials will be a combination of self-report (i.e., psychological resilience, trauma, alcohol misuse, depression, suicidality, burnout, and aggression), physiological (C-RP, IL-6, IL-10, TNF- $\alpha$ ), and behavioral (use of force reports, e.g. BlueTeam database) outcomes. Self-report measures will be collected via Qualtrics; psychophysiological data will be collected via a dried blood spot kit; and audio homework assignment data will be collected via Ilumivu; and study forms will be entered by the research team and stored electronically on REDCap. Behavioral data will be obtained from the database with the assistance of police department staff. Drs. [name] (Portland) and [name] (Albuquerque) will oversee data downloads from Qualtrics, REDCap, and Ilumivu as well as psychophysiological and behavioral data collection; a second research team member will verify that data downloads and collection were done correctly. The project manager will manage data storage.

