## **9.6 Data Analyses**

### Quantitative:

Following best practice guidelines including CONSORT feasibility guidelines and past research, we will measure sensitivity (using a relative efficiency approach) and

responsiveness to change (examining within-group change over time). Relative efficiency analyses will be used to establish that our outcome measures are sensitive to differences between our treatment arm of focus (MBRT) and our other two arms - an active control arm (SME) and a no-treatment control arm (NIC). Therefore, sensitivity analyses will focus on assessing the degree to which outcomes are sensitive to study arms and not whether change is significant. Sensitivity to differences for MBRT compared to SME and NIC will be assessed by examining the relative efficiency of each outcome variable for MBRT versus SME and NIC separately. We will calculate the relative efficiency for MBRT versus SME by conducting one-way, between-subjects Analysis of Covariance (ANCOVA) analyses with MBRT versus SME as the independent variable and each outcome variable at post-training as the dependent variable; we will include study site and gender as covariates. We will also conduct ANOVAs using the same independent and dependent variables to ensure that all inferential tests are conducted and identify any potential Type II Errors among the ANCOVAs. We will then divide the *F*-statistic for each behavioral (BlueTeam/departmental use of force; individual indicators of use of force as well as a composite score of use of force using the individual indicators), physiological (C-RP, IL-6, IL-10, TNF- $\alpha$ ), and self-report (aggression, alcohol misuse, depression, suicidal ideation, trauma symptoms, burnout, and psychological resilience) outcome by the largest *F*-statistic among these analyses, such that the larger the number, the more sensitive that outcome is to the impact of MBRT relative to the active control group.

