To calculate the relative efficiency of MBRT versus NIC, we will conduct one-way, between-subject ANCOVAs with MBRT vs. NIC as the independent variable, each outcome variable at post-training as the dependent variable, and gender and study site as covariates. Again, we will also conduct ANOVAs using the same independent and dependent variables to ensure all inferential tests are conducted and identify any potential Type II Errors among the ANCOVAs. We will then divide the *F*-statistic for each behavioral, physiological, and self-report outcome by the largest *F*-statistic among these analyses; again, the larger the number, the more sensitive the outcome is to MBRT relative to the no-treatment control group. These sensitivity analyses will allow assessment of which behavioral, physiological, and self-report outcomes are most sensitive to MBRT.

Responsiveness to change across time will be assessed in the MBRT arm for behavioral, physiological, and self-report outcomes by: 1) calculating and comparing standardized mean responses (SMR) for outcomes by subtracting the baseline mean response for each outcome from the post-intervention mean response for that outcome, and dividing by the standard deviation of change for that outcome; 2) calculating and comparing partial correlation coefficients (adjusting for study site and gender) between a global impression of change measure that captures the subjective experience of changes in stress, job performance, and resilience at post-intervention and residualized change scores (baseline to post-intervention) for each self-report outcome. For both SMR values and correlation coefficients, the higher the absolute value, the more responsive the outcome is to change across time in the MBRT arm. We will conduct additional correlation analyses using the same variables without adjusting for study site and gender to identify any potential Type II Errors among the partial correlations.

In addition, we will examine data for any indications of systematic site differences. Using baseline data (where sample size will be greatest) and pooling arms, since no treatment differences are expected at baseline, distributions of standardized responses on outcome measures will be summarized, graphed, and compared across sites. Key parameters, reliability

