estimates (i.e., Cronbach's alpha), and intraclass correlations will be estimated and checked for discrepancies between sites. Identified discrepancies will be investigated to determine site-specific issues that would undermine assumptions of conceptual and structural equivalence of measurement.

Given the optimization aim of our study, our analyses will not adjust for intraclass correlations across study arms (and any heterogeneity in those correlations). Our study will allow us to obtain information about the magnitude of intraclass correlations and the degree to which they are heterogeneous across study arms, which we will use for our data analysis plan in a future fully-powered efficacy RCT.

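### Aim 4.2 promises to confirm psychometric soundness, but the only reliability statistic named is Cronbach's alpha, which cannot be computed for the four blood markers or single use-of-force indicators and shows no stability over time

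*Combined protocol and SAP*

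**What the plan says.** Aim 4.2 (Précis, Objectives, 4) is to "Confirm sensitivity, responsiveness to change, and psychometric soundness of outcome measures". Soundness is listed there as something separate from sensitivity and responsiveness.

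Section 1.1, Objective 4, sets a benchmark for agreement between sites that includes "equivalence in outcome measure response distributions, reliability estimates, and intraclass correlations". It gives no minimum reliability.

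Section 9.6 (Quantitative) carries this out. Response distributions are compared across sites "Using baseline data (where sample size will be greatest) and pooling arms". The next sentence says that key parameters, reliability "estimates (i.e., Cronbach's alpha), and intraclass correlations will be estimated and checked for discrepancies between sites". A little further on, the same section says the study will yield "information about the magnitude of intraclass correlations and the degree to which they are heterogeneous across study arms", for use in planning the efficacy trial.

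The outcomes ranked in 9.6 are use of force, four blood markers and seven self-report domains. Use of force enters as "individual indicators of use of force as well as a composite score of use of force using the individual indicators", and 9.5 says likewise: "For behavioral data, we will analyze individual behavioral items as well as a composite score".

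Section 9.1 relies on past research for the reliability of the self-report and physiological measures. For use of force it describes the tracking system as the accepted standard and gives no reliability evidence.

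On available data, 5.1 states: "Participants randomized to the NIC condition will not receive any intervention, but will participate in the same assessments as the two active intervention conditions". The schedule in 6.1 has the blood markers at three visits, and the repeated questionnaires and the attention task at four.

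**The concern.** The aim covers the outcome measures as a whole, but the statistic chosen for it fits only multi-item scales. A blood marker is one number per visit, and so is a count of one type of use-of-force event. No repeat assay, between-visit correlation or record-agreement statistic is planned for either.

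Even for a questionnaire, alpha at one visit does not show whether an officer who receives nothing gets a similar score some weeks later. That is the property that matters for a measure intended to register change.

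At stake is how the rankings can be read. A low F-value or a small standardized response may mean that MBRT does not move the outcome, or that the outcome is measured noisily. Without a reliability estimate the two cannot be told apart. The blood markers and use of force are the most exposed, because the second responsiveness criterion in 9.6 (correlation with global impression of change) covers self-report outcomes only.

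**Working it through.** The plan gives no reliability figure to reproduce, so the check is a count, a reading of the intraclass correlations, and the precision of the remedy.

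**1. Where alpha can be computed (outcomes from 9.6).**
- Headings ranked: 1 use of force + 4 blood markers + 7 self-report = 12.
- Alpha cannot be computed for the 4 blood markers. Section 9.5 mentions composites for physiological outcomes, but 9.6 ranks the markers by name, and an alpha for a composite would not be the reliability of any one marker.
- For use of force, alpha can be computed for the composite but not for a single indicator. The documents do not fix the number of indicators. Assuming 3 to 6, each comparison ranks 3 + 1 + 4 + 7 = 15 to 6 + 1 + 4 + 7 = 18 F-values. Of these, 4 + 3 = 7 to 4 + 6 = 10 are single values with no alpha.
- The attention task is assessed at four visits but is not among the outcomes named for ranking. It has no stated reliability estimate either.

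**2. What the intraclass correlations are.** Section 9.6 lists them next to reliability, not as a form of it, and does not define them. Section 9.2 links the intraclass correlation to the number and size of clusters per arm in the future trial. Section 9.6 links it to heterogeneity across arms. Both uses are clustering. If the baseline wording in 9.6 also governs this sentence, which the text does not state outright, a single visit could not give a test-retest value.

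**3. Precision of a between-visit intraclass correlation.**
- Officers (arm sizes from 4.3, 20% attrition from 9.2): NIC 22 × 0.8 = 17.6, about 18; all arms 104 × 0.8 = 83.2, about 83.
- Approximate interval for two visits: z = atanh(r), SE = 1/√(n − 1.5), limits tanh(z ± 1.96 SE). The true value of 0.7 is an assumption, with z = 0.867.
- n = 18: SE = 1/√16.5 = 0.246; z from 0.385 to 1.350; interval **0.37 to 0.87**.
- n = 83: SE = 1/√81.5 = 0.111; z from 0.650 to 1.084; interval **0.57 to 0.79**.
- Exact F-based limits at n = 18 for other assumed values: 0.21 to 0.83 at 0.6; 0.37 to 0.88 at 0.7; 0.55 to 0.92 at 0.8.

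**4. What the plan already yields indirectly.** Responsiveness in 9.6 uses the SD of change in MBRT. With the baseline SD s1, post SD s2 and SD of change sd, the baseline-to-post correlation is r = (s1² + s2² − sd²)/(2·s1·s2). It can therefore be recovered for MBRT. Reporting it is not planned, and the responsiveness analysis does not extend to SME or NIC.

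**The case against.** The strongest reply has four parts.

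*The aim is being over-read.* Psychometric soundness is not defined, the Objective 4 benchmark is equivalence between sites, and that section says sensitivity and responsiveness decide which outcomes are kept. This stands in part. A reader might infer that reliability is the criterion for carrying an outcome forward; the documents do not say so. But soundness is named as something to confirm alongside the other two.

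*Unreliable measures are already penalized.* True: error lowers F. With an assumed true d of 0.5 and 38 against 28 officers (47 and 35 less 20%), λ = d² × reliability × 38 × 28/66 and expected F = 64(1 + λ)/62. That gives 4.78 at reliability 0.9 and 3.53 at 0.6. The penalty is applied without being seen, so the cause of a low rank stays unknown.

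*Past research and intraclass correlations cover the gap.* Section 9.1 does cite past research for self-report and physiological measures, but relying on it does not confirm soundness in this trial, and it gives no reliability evidence for use of force. The intraclass correlations are undefined. The interrater reliability in Objective 3 and 10.3.1 concerns session coders, not outcomes.

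*The remedy is weak.* The baseline-to-post interval is 8 weeks plus up to 21 days (6.2.4), so real change mixes with error, and the NIC interval is wide. Both points stand and limit what can be claimed.

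**Conclusion.** The point holds as a gap between a stated aim and its analysis. Alpha is the only statistic the plan names as reliability for outcome measures. It cannot serve the four blood markers or the single use-of-force indicators, and it does not address stability for any measure. This should be corrected, but it does not undermine the trial's other analyses.

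Two stronger readings are not supported. A reader might infer that use of force as a whole has no possible alpha, and so that five of the twelve headings lack one. Sections 9.5 and 9.6 plan a composite of several indicators, for which alpha is computable, though it would show internal consistency only. A reader might also infer that the trial cannot supply a baseline-to-post correlation for the efficacy trial's power calculation, and so attach a sample-size penalty to the gap. The correlation can be derived in MBRT from planned quantities; what is missing is a direct report, by arm.

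The conclusion assumes that the undefined intraclass correlations are clustering parameters, as their other uses suggest. If between-visit reliability was meant, the remedy is to say so. The precision figures assume a true value of 0.7 and 20% attrition.

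**What to change.** In 9.6:

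1. Keep Cronbach's alpha, restricted to the multi-item questionnaires.
2. Define the intraclass correlations already listed, stating that they are clustering parameters if that is the intent.
3. For every repeated outcome, including each blood marker and the attention task, add a between-visit intraclass correlation and a within-officer SD, both with 95% intervals. Estimate them from a mixed model with a random officer effect and arm-by-visit fixed effects, and report the NIC-only estimate alongside. The fixed effects remove average change; individual differences in response to training remain in the error term, which is why the untreated estimate is needed.
4. For use of force, correlate two halves of the pre-baseline record only if that record is long enough to split. The documents give the time to assemble it (1.1, Objective 2), not its length.
5. Report the baseline-to-post correlation by arm for the future power calculation.

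Place these results beside the sensitivity and responsiveness rankings, and label the estimates in item 3 as stability over the trial interval, not pure measurement error.

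The cost is SAP wording and a few additional models. Items 3 and 5 use assessments already scheduled; item 4 depends on the records available. The drawback is imprecision: the NIC-only intervals are too wide to confirm reliability on their own and must be reported as such.
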